2. SCHEDULE OF ACTIVITIES (SOA)

Procedure	Screening ¹		Treatment Period ²					Follow-up ¹
	Week -4	Week -2	Day 1	Day 15	Day 29 ³	Day 43	Day 57	Day 70
Informed Consent	X							
Entry Criteria	X ⁴	X ⁴	X ⁴					
Physical, Medical History, Demography, Height	X ^{5,9}	X ^{5,9}	X ^{5,9}					
Weight	X		X	X		X		
HemoCue Hgb	X	X	X	X	X	X	X	
eGFR	X							
Females: Urine Pregnancy Test ⁶	X		X		X		X	X
Females: Estradiol & FSH ⁷		X						
HIV screening and Hepcidin	X							
Randomization			X					
Administration of isotopic iron				X		X		
Blood sampling for isotopic iron					X	X	X	
Crossover ⁸					X			
ECG		X						X
Vital signs	X		X		X		X	X
Clinical chemistry & hematology ¹⁰	X							X
Urinalysis ¹⁰	X							X
Liver chemistry monitoring ¹¹				X		X		
Folate & Vitamin B ₁₂		X						
hsCRP		X						
Ferritin and TSAT		X						
Iron status markers ¹²			X	X	X	X	X	
Indices of erythropoiesis ¹³			X	X	X	X	X	
Blood draw for PGx			X					
AE and SAE Assessment ¹⁴	X ¹⁵	X ¹⁵	X	X	X	X	X	X
Review Concomitant Medications	X	X	X	X	X	X	X	X

- ¹ Allowable time window \pm 3 days.
- ² Allowable time window \pm 2 days.
- ³ All assessments to be performed **PRIOR** to crossing over.
- ⁴ Criteria to be assessed can be found in Section 9.4.1.
- ⁵ Complete physical examination, medical history & demography to be performed at Week -4, while a brief physical examination to be performed at Week -2 and Day 1.
- ⁶ Local urine testing will be standard for the protocol unless serum testing is required by local regulation or IRB/IEC.
- ⁷ As detailed in Inclusion Criteria.
- ⁸ Participants that had been administered daprodustat during treatment Period 1 will be switched to rhEPO, while those on rhEPO will be switched to daprodustat. Examples on switching are provided in the Study Reference Manual (SRM).
- ⁹ Height is only collected at Week -4.
- ¹⁰ Clinical laboratory assessments guidance can be found in Section 9.4.5
- ¹¹ Liver chemistry monitoring guidance can be found in Section 9.4.6.
- ¹² Iron status markers include serum iron, ferritin, transferrin, transferrin saturation (TSAT), soluble transferrin receptor, hepcidin and erythroferrone and are described in Section 9.8.2. All samples for iron status markers to be taken pre dose.
- ¹³ Indices of erythropoiesis include Hgb, hematocrit, red blood cell number, mean corpuscular volume, reticulocyte Hgb and reticulocyte number and are described in Section 9.8.3.
- ¹⁴ Guidance on the timing and need for collection of AEs & SAEs are described in Section 9.2.

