At Day 29 participants will be crossed over to the study treatment they did not receive in Treatment Period 1, i.e., for participants that remained on their current therapy they would be switched to daprodustat, while subjects that had been administered daprodustat would be switched back to their previous therapy at the dose prior to randomization. At 2 weeks following initiation of dosing, participants will again be administered ferrous sulfate containing the stable iron isotope not administered following the assessment in Treatment Period 1 orally. Two weeks following oral iron administration a blood sample will again be taken in order to assess the incorporation of the iron isotope into red blood cells by TIMS.

Participants will attend a follow-up visit 14 ± 3 days following the final blood sample for assessment of red blood cell iron.

Table 1 Possible Treatment Sequences

	Sequence A N=3	Sequence B N=3	Sequence C N=3	Sequence D N=3
Treatment Period 1	rhEPO ⁵⁷ Fe	rhEPO ⁵⁸ Fe	Daprodustat ⁵⁷ Fe	Daprodustat ⁵⁸ Fe
Treatment Period 2	Daprodustat ⁵⁸ Fe	Daprodustat ⁵⁷ Fe	rhEPO ⁵⁸ Fe	rhEPO ⁵⁷ Fe

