6.1. Inclusion Criteria

Participants are eligible to be included in the study only if all the following criteria apply:

Age

1. Participant must be at least 18 years of age inclusive, at the time of signing the informed consent.

Type of Participant and Disease Characteristics

2. Participants who are Stage 3, 4 or 5 CKD (confirmed at Week -4 only) defined by eGFR using the CKD Epidemiology Collaboration (CKD-EPI) formula ([Levey, 2009](#)). See the Study Reference Manual (SRM) for details on calculation.

3. Participants who are currently treated with stable doses ($\leq 50\%$ change in 4-weekly dose) for at least 8 weeks prior to and including the screening period, of rhEPO (i.e., epoetin alfa or darbepoetin alfa).
4. Participants with Hgb levels between 9.0 and 11.5 g/dL, inclusive, who meet the Hgb stability criteria as outlined in Section 6.2.1.
5. Participants may be on stable maintenance oral iron supplementation ($<50\%$ change in overall dose and compliance of 80% of prescribed doses in the 4 weeks prior to and including the screening period). If participants have been on IV iron, then participants will not have received IV iron for 8 weeks prior to the Day 1 visit.

Sex

6. Male or female

a. Female participants:

A female participant is eligible to participate if she is not pregnant (see [Appendix 7](#)), not breastfeeding, and at least one of the following conditions applies:

- (i) Not a woman of childbearing potential (WOCBP) as defined in [Appendix 7](#)

OR

- (ii) A WOCBP who agrees to follow the contraceptive guidance in [Appendix 7](#) during the treatment period to the follow-up visit.

Informed Consent

7. Capable of giving signed informed consent as described in [Appendix 5](#) which includes compliance with the requirements and restrictions listed in the informed consent form (ICF) and in this protocol.

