8.2.1.1. Hgb Stopping Criteria

GSK will supply a point-of-care Hgb analyzer (HemoCue) to each site for rapid and convenient monitoring of Hgb levels and to ensure consistency of Hgb measurements across sites participating in the study.

Blood samples for measurement of Hgb concentrations via HemoCue will be collected and recorded in the eCRF. [Table 3](#) summarizes the Hgb values and corresponding action to be taken at each visit.

Table 3 Hgb Stopping Criteria

Hgb (g/dL) at visit		Action
<7.5		Repeat HemoCue assessment on the same sample at same study visit to confirm; take average of 2 values. If confirmed, permanently discontinue study treatment and withdraw participant from the study.
≥7.5 - <13.0 With:	≥2.0 g/dL decrease in Hgb over the previous 2 weeks	Repeat HemoCue assessment on the same sample at same study visit to confirm; take average of 2 values. If confirmed, permanently discontinue study treatment and withdraw participant from the study.
≥7.5 - <13.0 With:	<1.0 absolute change in Hgb over the previous 2 weeks	Continue study treatment.
≥7.5 - <13.0 With:	≥1.0 increase in Hgb over the previous 2 weeks	Repeat HemoCue assessment on the same sample at same study visit to confirm; take average of 2 values. If confirmed, permanently discontinue study treatment and withdraw participant from the study.
≥13.0		Repeat HemoCue assessment on the same sample at same study visit to confirm; take average of 2 values. If confirmed, permanently discontinue study treatment and withdraw participant from the study.

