Study intervention Assignment	
Participants will be randomly assigned either to remain on their current therapy (either epoetin alfa or darbepoetin alfa) or be switched to daprodustat for Treatment Period 1.
 
For assessment of incorporation of iron into erythrocytes, enrolled participants will be administered ferrous sulfate containing a stable isotope of iron (57Fe or 58Fe) orally in a randomized fashion following 2 weeks of administration of randomized study treatment. Two weeks following oral iron administration a blood sample will be taken in order to assess the incorporation of the iron isotope into red blood cells by thermal ionization mass spectrometry(TIMS).
 
At Day 29 participants will be crossed over to the study treatment they did not receive in Treatment Period 1. At 2 weeks following initiation of dosing, participants will again be administered ferrous sulfate containing the stable iron isotope not administered following the assessment in Treatment Period 1 orally. Two weeks following oral iron administration a blood sample will again be taken in order to assess the incorporation of the iron isotope into red blood cells by TIMS.
 
Participants will attend a follow-up visit 14 ± 3 days following the final blood sample for assessment of red blood cell iron.
 
There are 4 possible treatment sequences:
 
Possible Treatment Sequences:
 
  
 	Sequence A N=3	Sequence B N=3	Sequence C N=3	Sequence D N=3	
   
 Treatment Period 1	rhEPO 57Fe	rhEPO 58Fe	Daprodustat 57Fe	Daprodustat 58Fe	
 
 Treatment Period 2	Daprodustat 58Fe	Daprodustat 57Fe	rhEPO 58Fe	rhEPO 57Fe	
  
		Sequence A N=3	Sequence B N=3	Sequence C N=3	Sequence D N=3	Treatment Period 1	rhEPO 57Fe	rhEPO 58Fe	Daprodustat 57Fe	Daprodustat 58Fe	Treatment Period 2	Daprodustat 58Fe	Daprodustat 57Fe	rhEPO 58Fe	rhEPO 57Fe
	Sequence A N=3	Sequence B N=3	Sequence C N=3	Sequence D N=3												
Treatment Period 1	rhEPO 57Fe	rhEPO 58Fe	Daprodustat 57Fe	Daprodustat 58Fe												
Treatment Period 2	Daprodustat 58Fe	Daprodustat 57Fe	rhEPO 58Fe	rhEPO 57Fe												
Interim Analysis	
 • No interim analysis will be performed in this study. 															

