4.2.1. Definition of endpoint(s)

Objectives	Endpoints
Primary Objectives	Primary Endpoints

 Compare the efficacy of daprodustat to rhEPO (i.e., epoetin alfa or darbepoetin alfa) on iron absorption 	
 Difference in fractional oral iron absorption (%) between daprodustat and rhEPO

The process for calculating the fractional iron absorption will depend on the sequence and is defined separately for each iron isotope. Formulas will be based on IAEA guidance for assessment of iron bioavailability in humans (IAEA 2012).

Sequences A and C:

S. No.	Parameters	Period 1 - ⁵⁷ Fe Fractional Oral Iron Absorption	Period 2 - ⁵⁸ Fe Fractional Oral Iron Absorption	Details
Parameters provided in data				
1	Hgb in g/dL	Hgb Day 15	Hgb Day 43	We will use the Hgb (g/dL) measurement from the day of isotope dosing (Day 15 for Period 1, Day 43 for Period 2)
2	BV in mL	70 * Day 15 Weight	70 * Day 43 Weight	We will assume a blood volume (BV) of 70 mL/kg and a fixed volume per kg. Weight represents the

S. No.	Parameters	Period 1 - ⁵⁷ Fe Fractional Oral Iron Absorption	Period 2 - ⁵⁸ Fe Fractional Oral Iron Absorption	Details
				weight measurement (kg) taken on the day of dosing (Day 15 for Period 1, Day 43 for Period 2).
3a	Baseline ⁵⁷ Fe/ ⁵⁶ Fe	0.02317	N/A	Natural abundance measure for iron isotope, which is an assumed constant for this analysis.
3b	Baseline ⁵⁸ Fe/ ⁵⁶ Fe	N/A	Value3b	Baseline measurement for ⁵⁸ Fe in

S. No.	Parameters	Period 1 - ⁵⁷ Fe Fractional Oral Iron Absorption	Period 2 - ⁵⁸ Fe Fractional Oral Iron Absorption	Details
				
Period 2 will utilize the Day 43 blood sampling for isotopic iron, as the ⁵⁷Fe solution in Period 1 may contain small quantities of ⁵⁸Fe. This measurement will be provided by Cornell University.

4a	Enriched ⁵⁷ Fe/ ⁵⁶ Fe	Value4a	N/A	Enriched iron value is calculated internally on the

S. No.	Parameters	Period 1 - ⁵⁷ Fe Fractional Oral Iron Absorption	Period 2 - ⁵⁸ Fe Fractional Oral Iron Absorption	Details
				spectroscopy instrument and provided by Cornell University.
4b	Enriched ⁵⁸ Fe/ ⁵⁶ Fe	N/A	Value4b	Enriched iron value is calculated internally on the spectroscopy instrument and provided by Cornell University.
Parameters derived by S&P				
5	% excess	$\frac{\text{Value4a} - \text{Value3a}}{\text{Value3a}} * 100$	$\frac{\text{Value4b} - \text{Value3b}}{\text{Value3b}} * 100$	S&P will derive this value. Δ% excess is used

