S. No.	Parameters	Period 1 - ⁵⁷ Fe Fractional Oral Iron Absorption	Period 2 - ⁵⁸ Fe Fractional Oral Iron Absorption	Details
				to express measurements of enrichment relative to baseline. We will use the following formula suggested by the IAEA for the assessment of iron bioavailability (IAEA pg.20).
6	Total circulating Fe (mg)	$Hgb * BV * 3.47 * 0.01$	$Hgb * BV * 3.47 * 0.01$	S&P will derive this value, using the formula

S. No.	Parameters	Period 1 - ⁵⁷ Fe Fractional Oral Iron Absorption	Period 2 - ⁵⁸ Fe Fractional Oral Iron Absorption	Details
				suggested by the IAEA for the assessment of iron bioavailability (IAEA pg.33).
7	Total incorporated iron isotope (mg)	$Total\ incorporated\ ^{57}Fe = Parameter5 * Parameter6 * 0.00287$	$Total\ incorporated\ ^{58}Fe = Parameter5 * Parameter6 * 0.0214$	S&P will derive this value. We assume the fractional abundance of ⁵⁷ Fe in mg is (0.0214 g * 0.01), and the fractional abundance of ⁵⁸ Fe in mg is (0.00287 g *

S. No.	Parameters	Period 1 - ⁵⁷ Fe Fractional Oral Iron Absorption	Period 2 - ⁵⁸ Fe Fractional Oral Iron Absorption	Details
				0.01).
8	% iron isotope incorporated	$\% \text{ } ^{57}\text{Fe Incorporated} = \frac{\text{Parameter 7}}{\text{ } ^{57}\text{Fe Dose}}$	$\% \text{ } ^{58}\text{Fe Incorporated} = \frac{\text{Parameter 7}}{\text{ } ^{58}\text{Fe Dose}}$	
S&P will derive percent of iron isotope incorporated. ⁵⁷Fe and ⁵⁸Fe doses (mg) will be determined using the density of ferrous sulfate (FeSO₄) oral solution (1g/mL), the dose of oral solution (in mL),

S. No.	Parameters	Period 1 - ⁵⁷ Fe Fractional Oral Iron Absorption	Period 2 - ⁵⁸ Fe Fractional Oral Iron Absorption	Details
				and concentration of elemental iron (1mg/mL).
9	Assumed % iron isotope absorbed if 80%	$\% \text{ } ^{57}\text{Fe absorbed} = \text{Parameter 8} * \frac{100}{80}$	$\% \text{ } ^{58}\text{Fe absorbed} = \text{Parameter 8} * \frac{100}{80}$	S&P will derive this value, using the formula suggested by the IAEA for the assessment of iron bioavailability (IAEA pg.38). Parameter 9 defines the fractional oral iron absorption

S. No.	Parameters	Period 1 - ⁵⁷ Fe Fractional Oral Iron Absorption	Period 2 - ⁵⁸ Fe Fractional Oral Iron Absorption	Details
				endpoint, assuming 80% of the absorbed Fe is incorporated into RBCs.

Sequences B and D:

S. No.	Parameters	Period 1 - ⁵⁸ Fe Fractional Oral Iron Absorption	Period 2 - ⁵⁷ Fe Fractional Oral Iron Absorption	Details
Parameters provided in data				

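### The absorption formula pairs dosing-day Hgb with enrichment measured about 14 days later, so Hgb drift that differs by treatment biases the comparison modestly

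*SAP*

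**What the plan says.** SAP 4.2.1 builds the primary endpoint from nine parameters. Four matter here.

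- **Parameter 1 (Hgb).** "We will use the Hgb (g/dL) measurement from the day of isotope dosing", meaning Day 15 in Period 1 and Day 43 in Period 2. The tables for Sequences A and C and for B and D say the same.
- **Parameter 2 (blood volume).** "We will assume a blood volume (BV) of 70 mL/kg and a fixed volume per kg", using weight from the dosing day.
- **Parameter 6 (circulating iron).** "Hgb * BV * 3.47 * 0.01", which is linear in Hgb.
- **Parameter 7 (incorporated isotope).** Percent excess (Parameter 5) times Parameter 6 times constants. Parameters 8 and 9 then divide by the dose and by 80%.

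The enriched ratio in Parameter 5 comes from a later sample. SAP 1.2 says of Period 1: "Two weeks following oral iron administration a blood sample will be taken in order to assess the incorporation of the iron isotope". Protocol 5.1 says of Period 2: "Two weeks following oral iron administration a blood sample will again be taken in order to assess the incorporation of the iron isotope". The Schedule of Activities puts these samples on Day 29 and Day 57, with a window of ±2 days.

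Hgb is also scheduled on those two days, by HemoCue and in the erythropoiesis panel ("Indices of erythropoiesis include Hgb, hematocrit, red blood cell number"). The derivation does not use it. The only planned sensitivity analysis (SAP 4.2.3) repeats the model in the mITT population. The SAP cites IAEA guidance for its formulas but gives no reason for taking Hgb on the dosing day.

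**The concern.** The isotope in circulation when blood is drawn equals the enrichment of red-cell iron at that moment times the red-cell iron present at that moment. Parameter 7 takes the two factors from different days. If red-cell iron grows between dosing and sampling, the label is diluted, enrichment falls, and the smaller dosing-day iron mass does not restore it, so absorption is understated. If red-cell iron shrinks, absorption is overstated.

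Drift could differ by treatment. rhEPO is a dose the participant is already stable on, whereas daprodustat is a switch. Protocol Table 2 assigns a single daprodustat dose to darbepoetin doses spanning a tenfold range, and Protocol 5.5 aims for unchanged Hgb on average, not in each participant. An error that follows treatment is not removed by the period and isotope terms in SAP 4.2.2.

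The stopping rules limit drift without excluding it from the analysis. The Evaluable Population has no Hgb condition, and a change found on Day 57 is found at the visit when the last absorption sample is due. The mITT set can also include a participant withdrawn on Day 29 for Hgb change, if the Period 1 assessment was completed.

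**Working it through.** **The plan's own figure.** Protocol 10.2 and SAP 5 state 90% power with 12 participants, a difference of 11 points and SD 10.7. A two-sided 5% paired t-test with 11 degrees of freedom and noncentrality 11 × √12 / 10.7 = 3.56 gives 89.9%, so the figure reproduces.

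**Inputs.**
- Illustrative absorption on rhEPO: 14.71% (Protocol 5.4, fasted healthy women).
- Relevant change: 30% (Protocol 5.4), read as relative, so 0.30 × 14.71 = 4.41 points.
- Entry Hgb: "Participants with Hgb levels between 9.0 and 11.5 g/dL, inclusive". Hgb 10 is used as a central value.
- Table 3 in Protocol 8.2.1.1 withdraws participants for a confirmed "≥1.0 increase in Hgb over the previous 2 weeks" or a fall of at least 2.0 g/dL. It explicitly continues treatment only for an absolute change below 1.0. It lists no action for a fall of 1.0 to just under 2.0.
- Size of drift: not given in the documents, so a range is shown.

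**Error in one value.** Parameters 5 to 9 form a product and only Parameter 6 contains Hgb. With blood volume fixed, the SAP value divided by the value using sampling-day Hgb equals Hgb(dosing)/Hgb(sampling).

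At dosing-day Hgb 10:
- rise of 0.99: 10/10.99 - 1 = -9.0%
- fall of 0.99: 10/9.01 - 1 = +11.0%
- fall of 1.99 (the range with no listed action): 10/8.01 - 1 = +24.8%

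For drift below 1.0 in either direction, the range is -9.9% to +12.4% at Hgb 9.0 (9/9.99, 9/8.01) and -7.9% to +9.4% at Hgb 11.5 (11.5/12.49, 11.5/10.51).

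**Bias in the treatment contrast, drift on daprodustat only.** Let f = 10/(10 + drift), applied to every daprodustat value, with rhEPO stable at 14.71%. The null difference becomes 14.71 × (f - 1). A true 11 points becomes 25.71 × f - 14.71. Rejection rates use the paired t-test above with SD 10.7.

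| Drift (g/dL) | f | Null difference (points) | Null rejection rate | True 11 becomes | Power |
|---|---|---|---|---|---|
| -1.0 | 1.1111 | +1.63 | 7.7% | 13.86 | 98.2% |
| -0.5 | 1.0526 | +0.77 | 5.6% | 12.35 | 95.3% |
| 0 | 1 | 0 | 5.0% | 11.00 | 89.9% |
| +0.5 | 0.9524 | -0.70 | 5.5% | 9.78 | 82.1% |
| +0.99 | 0.9099 | -1.33 | 6.8% | 8.68 | 72.6% |

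**Same drift on both treatments.** The difference is multiplied by f. Zero stays zero. A true 11 becomes 10.48 at +0.5 and 11.58 at -0.5.

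**The case against.** **The design works against differential drift.** Entry requires stable Hgb, rhEPO stays at its established dose, the switching algorithm aims to leave Hgb unchanged, and a needed dose change means withdrawal. The drift that matters must also arise in the second fortnight of a period. This stands: no mean drift can be read from the documents, and every row of the table is an assumption.

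**The effect is small.** At +0.5 g/dL the null bias of -0.70 is 0.70/3.09 = 0.23 of the planned standard error (10.7/√12 = 3.09) and 16% of 4.41 points. This also stands. The power loss, from 89.9% to 82.1%, is moderate.

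**Sampling-day Hgb is not always better.** If Hgb concentration moves only because plasma volume changes, red-cell iron is unchanged and the later Hgb brings in the error. This is a real limit. It gives no positive reason to prefer dosing-day Hgb, though, because the fixed 70 mL/kg model already reads any Hgb change as a change in red-cell iron.

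**Stronger readings a reader might infer.**
- *That errors up to +25% are permitted.* Table 3 does not say that a fall of 1.0 to just under 2.0 g/dL continues. It says nothing, and its rows need to be reconciled.
- *That any drift biases the comparison.* Individual drift unrelated to treatment adds mainly noise, and common drift only rescales a true difference.
- *That the choice favours daprodustat.* A rise on daprodustat biases against it. Only a fall relative to rhEPO would inflate the difference.
- *That the SAP departs from its cited guidance.* That guidance cannot be checked from these documents.

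**Conclusion.** The timing mismatch is in the SAP text, and the scaling by Hgb(dosing)/Hgb(sampling) follows from its own formula. For drift that Table 3 explicitly continues, the error in a single value at Hgb 10 is about -9% to +11%. For the contrast, a daprodustat-only drift between -1.0 and +0.99 g/dL shifts a null difference by about +1.6 to -1.3 points and turns a true 11 points into about 13.9 to 8.7. The lower end, -1.0, lies just outside the range explicitly continued.

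These figures assume Hgb 10 at dosing, rhEPO absorption of 14.71%, the same drift in every participant, and drift in red-cell mass rather than plasma volume. Since the design aims for no mean Hgb change, the likely bias is modest. Severity is minor to moderate: the point does not undermine the primary comparison, but it is an avoidable error in the primary endpoint that data already scheduled can largely remove.

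**What to change.** Before results are seen, amend Parameter 1 in both tables of SAP 4.2.1 so that Parameter 6 uses central-laboratory Hgb from the enrichment-sample visit: Day 29 for Period 1 and Day 57 for Period 2. Keep dosing-day weight in Parameter 2. Add the dosing-day Hgb version to SAP 4.2.3 as a pre-specified sensitivity analysis. If the cited guidance prescribes dosing-day Hgb, the SAP should say so.

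The change costs SAP wording and one programming line, with no new data. Under the fixed-volume model it sets the scaling factor to 1, so the expected difference stays at 11 points and power at 89.9%.

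There are two downsides. Weight is scheduled within the periods only on Days 15 and 43, so Hgb and weight will come from different days. A change in Hgb due only to plasma volume is not corrected.

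Separately, the rows of Protocol Table 3 should be reconciled so that a 2-week fall of 1.0 to just under 2.0 g/dL is addressed; which action applies is for the sponsor to state.

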7.1.1. Daprodustat Dosing Information

Doses of daprodustat to be administered are based on the rhEPO dose at randomization (Day 1) as described in [Table 2](#).

Table 2 Daprodustat Doses

Darbepoetin alfa ($\mu\text{g}/4$ wk SC/IV)	Epoetin alfa (convert SC to IV U/week) ¹	Daprodustat dose (mg, once daily)
20 to 30	1500 to 2000	1
>30 to 300	>2000 to <20000	2
>300	≥ 20000	4

¹ Standardized rhEPO IV dose (U/week) = $161/113 \times (\text{epoetin SC dose (units)/frequency})$

7.1.2. rhEPO Dosing Information

Participants are required to be currently treated with stable doses ($\leq 50\%$ change in 4-weekly dose) of rhEPO for at least 8 weeks prior to and including the screening period. The dose of rhEPO to be administered during the study as randomized study treatment will be the rhEPO dose at randomization (Day 1). This dose is to be administered whether a participant is randomized to rhEPO on Treatment Period 1, or is switching back to rhEPO following 4 weeks of administration of daprodustat on Treatment Period 2.

7.1.3. ⁵⁷Fe Dosing Information

An oral solution will be administered containing 10 mg of ⁵⁷Fe as ferrous sulfate. Exact doses will be measured, calculated, and captured for each individual participant. The solution is to be taken following an overnight fast. Further details will be outlined in the compounding document and SRM.

7.1.4. ⁵⁸Fe Dosing Information

An oral solution will be administered containing 3 mg of ⁵⁸Fe as ferrous sulfate with 7 mg of ⁵⁶Fe as ferrous sulfate (natural abundance Fe). Exact doses will be measured, calculated, and captured for each individual participant. The solutions are to be taken following an overnight fast. Further details will be outlined in the compounding document and SRM.

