7	Total incorporated iron isotope (mg)	$Total\ incorporated\ ^{58}Fe = Parameter5 * Parameter6 * 0.0214 * 0.50797$	$Total\ incorporated\ ^{57}Fe = Parameter5 * Parameter6 * 0.0214 * 0.49203$	S&P will derive this value. We assume

S. No.	Parameters	Period 1 - ⁵⁸ Fe Fractional Oral Iron Absorption	Period 2 - ⁵⁷ Fe Fractional Oral Iron Absorption	Details
				the fractional abundance of ⁵⁷ Fe in mg is (0.0214 g * 0.01), and the fractional abundance of ⁵⁸ Fe in mg is (0.00287 g * 0.01).
8	% iron isotope incorporated	$\% \text{ } ^{58}\text{Fe Incorporated} = \frac{\text{Parameter7}}{58\text{Fe Dose}}$	$\% \text{ } ^{57}\text{Fe Incorporated} = \frac{\text{Parameter7}}{57\text{Fe Dose}}$	S&P will derive percent of iron isotope incorporated. ⁵⁷ Fe and ⁵⁸ Fe doses (mg) will be determined using the

S. No.	Parameters	Period 1 - ⁵⁸ Fe Fractional Oral Iron Absorption	Period 2 - ⁵⁷ Fe Fractional Oral Iron Absorption	Details
				density of ferrous sulfate (FeSO ₄) oral solution (1g/mL), the dose of oral solution (in mL), and concentration of elemental iron (1mg/mL).
9	Assumed % iron isotope absorbed if 80%	$\% \text{ } ^{58}\text{Fe absorbed} = \text{Parameter8} * \frac{100}{80}$	$\% \text{ } ^{57}\text{Fe absorbed} = \text{Parameter8} * \frac{100}{80}$	S&P will derive this value, using the formula suggested by the IAEA for the assessment

S. N o.	Para meter s	Period 1 - ⁵⁸ Fe Fractional Oral Iron Absorption	Period 2 - ⁵⁷ Fe Fractional Oral Iron Absorption	Detail s
				of iron bioavailability (IAEA pg.38). Parameter 9 defines the fractional oral iron absorption endpoint, assuming 80% of the absorbed Fe is incorporated into RBCs.

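### Parameter 7 of the primary endpoint swaps the 57Fe and 58Fe abundances in Sequences A/C and uses 0.0214 with undefined factors for both isotopes in B/D, so every absorption value is wrong if programmed as written

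*SAP*

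**What the plan says.** SAP 4.2.1 derives fractional absorption in nine numbered parameters, in one table for Sequences A and C and another for B and D. Parameter 5 is the percent excess of the isotope ratio over baseline. Parameter 6 is circulating iron, "Hgb * BV * 3.47 * 0.01". Parameter 7 multiplies these two by a constant to give incorporated isotope in mg. Parameter 8 divides by the isotope dose. Parameter 9 multiplies by 100/80 and is the primary endpoint.

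The constants in the Parameter 7 formulas are:

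- Sequences A/C, 57Fe (Period 1): "Parameter5 * Parameter6 * 0.00287"
- Sequences A/C, 58Fe (Period 2): "Parameter5 * Parameter6 * 0.0214"
- Sequences B/D, 58Fe (Period 1): "Parameter5 * Parameter6 * 0.0214 * 0.50797"
- Sequences B/D, 57Fe (Period 2): "Parameter5 * Parameter6 * 0.0214 * 0.49203"

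The Details column of the same row assigns the constants differently. It states "fractional abundance of ⁵⁷ Fe in mg is (0.0214 g * 0.01" and gives 0.00287 g × 0.01 for 58Fe. Its text is the same in both tables.

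**The concern.** Incorporated isotope should be the percent excess times circulating iron times the natural abundance of that same isotope. In A/C each isotope is given the other's abundance. In B/D both isotopes are given the 57Fe value, scaled by 0.50797 or 0.49203. These two factors sum to 1 and are neither defined nor used anywhere else. The same isotope is therefore converted differently in different sequences, and none of the four formulas agrees with the abundances stated beside it.

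The errors are multiplicative and feed straight into the primary endpoint. The treatment estimate and its confidence interval, both in absorption points, would be on the wrong scale and could not be read against the 11-point difference used to size the trial.

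**Working it through.** **Inputs.** Abundances 0.0214 (57Fe) and 0.00287 (58Fe), baseline ratios 57Fe/56Fe 0.02317 and 58Fe/56Fe 0.00307, blood volume 70 mL/kg, and 80% incorporation: SAP 4.2.1. Isotope doses 10 mg 57Fe and 3 mg 58Fe: Protocol 7.1.3 and 7.1.4. Fasted mean absorption 14.71%, SD 10.7: Protocol 5.4. Planning difference 11 points, 12 participants: Protocol 10.2. The body weight and Hgb in step 3 are illustrative and cancel out.

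**1. The plan's own figure.** For a two-sided paired t-test at 0.05, the noncentrality is (11/10.7) × √12 = 3.56 on 11 df, giving power 89.9% against the stated 90%. The sample size calculation reproduces and is not at issue.

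**2. Which isotope takes which constant.** An isotope's abundance divided by its ratio to 56Fe should give the 56Fe share, which must be below 1 and nearly the same for both isotopes.

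- Details order: 0.0214/0.02317 = 0.924 and 0.00287/0.00307 = 0.935. These are consistent.
- A/C formulas: 0.00287/0.02317 = 0.124 and 0.0214/0.00307 = 6.97. The second is impossible.
- B/D formulas: 0.0214 × 0.50797 = 0.010871, and 0.010871/0.00307 = 3.54, also impossible; 0.0214 × 0.49203 = 0.010529, and 0.010529/0.02317 = 0.454.

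So the Details column has the right order. No simple ratio, share or three-term product of the SAP's constants that was tried gives 0.50797 or 0.49203.

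**3. Error in each formula.** Multiplier = constant as written / abundance in Details. Example: Hgb 10 g/dL, 70 kg, so blood volume is 4900 mL and circulating iron is 10 × 4900 × 3.47 × 0.01 = 1700.3 mg. A true absorption of 14.71% incorporates 0.1471 × 0.8 × 10 = 1.177 mg 57Fe (excess 3.234%) or 0.1471 × 0.8 × 3 = 0.353 mg 58Fe (excess 7.235%).

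| Formula | Multiplier | Parameter 9 with Details constants | Parameter 9 as written |
|---|---|---|---|
| A/C, 57Fe | 0.00287/0.0214 = 0.134 | 14.71% | 1.97% |
| A/C, 58Fe | 0.0214/0.00287 = 7.456 | 14.71% | 109.7% |
| B/D, 58Fe | 0.010871/0.00287 = 3.788 | 14.71% | 55.7% |
| B/D, 57Fe | 0.010529/0.0214 = 0.492 | 14.71% | 7.24% |

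The multipliers do not depend on Hgb or weight. In A/C, any true 58Fe absorption above 100/7.456 = 13.4% is returned as more than 100%.

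**4. Effect on the treatment estimate.** Within A/C the treatment contrast is scaled by (7.456 + 0.134)/2 = 3.80; within B/D by (3.788 + 0.492)/2 = 2.14. With three participants per sequence the average is 2.97, so a true +11 is estimated at about 2.97 × 11 = 32.6. With unequal evaluable numbers the scale would lie between 2.14 and 3.80.

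**5. Effect on precision and power.** Simulation of 20,000 trials: 12 participants, three per sequence, within-participant differences with treatment, period and isotope terms; normal data with mean 14.71, SD 10.7 and paired-difference SD 10.7.

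| Constants | Mean estimate, true +11 | SE | Power | Type I error |
|---|---|---|---|---|
| Correct | 11.0 | 3.1 | 89% | 5.1% |
| As written | 32.4 | 17.8 | 37% | 4.7% |

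Under an alternative assumption (lognormal data, mean 14.71, SD 10.7, 75% increase, log-scale correlation 0.5 to 0.7), power falls from about 60–80% to about 22%.

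**6. Units.** Parameter 5 already carries × 100, so Parameter 7 is 100 times the mg value (117.7 for 1.177 mg of 57Fe with correct constants). The Details column has × 0.01, which the formulas omit; Parameter 8 is called a percentage but has no × 100. The two omissions cancel, so Parameter 9 is in percent. This is a labelling fault, separate from the wrong constants.

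**The case against.** Five points can be made for the plan.

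- **The equations may be misread.** They sit in table cells that copy badly from a PDF, so 0.50797 and 0.49203 should be confirmed on the typeset page. If both are artefacts, B/D 57Fe becomes correct, but B/D 58Fe becomes wrong by 7.456 and both A/C formulas stay wrong. Three of four would still be in error, with a mean multiplier of (0.134 + 7.456 + 7.456 + 1)/4 = 4.01. The A/C swap is unlikely to be a misreading, because both constants match the Details column digit for digit.
- **The code may be right.** The Details column has the correct order, and SAP Section 1 leaves further data handling to a separate programming specification that is not available. This stands as a limit: reported values are wrong only if the formulas are programmed literally. It does not cure a wrong rule in the document that defines the endpoint.
- **The model absorbs part of the error.** This is correct under the null. A and C share one isotope-by-period pattern and B and D the other, so the period and isotope terms fit both average shifts. Simulated type I error was 3.4–4.5% with equal and with several unequal sequence sizes. The terms do not restore the scale of the effect or the lost precision.
- **The power loss depends on assumptions.** This is accepted. The lognormal shape and correlations are not in the documents, so power as written is best given as a range of about 22% to 38%.
- **Period 2 uses a measured Day 43 baseline.** Multiplying by natural abundance is exact only if that baseline is still at the natural ratio. This is a fair caveat on the recovery check in step 3, which assumes it. It does not account for the swap.

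**Conclusion.** The concern holds: Parameter 7 is wrong as written and must be corrected before the endpoint is derived. All four formulas conflict with the SAP's own stated abundances, by factors of 0.134, 7.46, 3.79 and 0.492. The harm is an estimate inflated about threefold, a standard error nearly six times too large (17.8 against 3.1), individual values above 100%, and power of about 22% to 38%. False positives are not increased. The multipliers follow from the SAP's constants alone. The threefold inflation assumes equal sequence sizes, and the power figures rest on the simulation assumptions given above. All of it assumes that the formulas are programmed as printed.

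**What to change.** In both tables and both periods, set total incorporated 57Fe = Parameter 5 × Parameter 6 × 0.0214 and total incorporated 58Fe = Parameter 5 × Parameter 6 × 0.00287. Check 0.50797 and 0.49203 against the typeset page, then delete them or state their derivation and purpose.

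Apply the 0.01 once. Either keep Parameter 7 in mg by including × 0.01 and add × 100 to Parameter 8, or keep the present scaling and drop the mg label.

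Add a worked check that a known absorption is returned unchanged for each isotope in all four sequences, including a Period 2 case with a Day 43 baseline slightly above the natural ratio. Confirm that the derivation code and the programming specification use the same constants.

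The cost is SAP wording and derivation code. No new data, visits or participants are needed.
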